### ***Statistical analysis***

Numerical data will be explored for normality by checking the distribution of data and using tests of normality (Kolmogorov-Smirnov and Shapiro-Wilk tests). Data will be presented as mean, median, standard deviation (SD), minimum, maximum and 95% Confidence Interval (95% CI) for the mean values. For parametric data, paired t-test will be used to compare between actual soft tissue measurement and software measurement. For non-parametric data, Wilcoxon signed-rank test will be used to compare between actual soft tissue measurement and software measurement. Inter- and intra-examiner reliability will be assessed using Cronbach's alpha and Intra-Class Correlation coefficients.

The significance level will be set at  $P \leq 0.05$ . Statistical analysis will be performed with IBM® SPSS® Statistics Version 20 for Windows.

---

\* IBM Corporation, NY, USA.

\* SPSS, Inc., an IBM Company.

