### ***Sample size calculation***

Based upon the assumption that we need to reach 90% accuracy, in light of the results of Resnick CM et al (2016), the computed effect size for the accuracy of linear measurements was found to be (1.05), using alpha ( $\alpha$ ) level of (5%) and Beta ( $\beta$ ) level of (20%) i.e. power = 80%; the study will include 10 subjects. To compensate for 15% for the use of non-parametric tests; the final minimum estimated sample size will be 12 subjects. Sample size calculation was performed using G\*Power Version 3.1.9.2.

Patients to be included:

- a) Patients who have class III facial deformity to be corrected using bimaxillary orthognathic surgery.
- b) No medical problems that might interfere with general anesthesia or interfere with bone and soft tissue healing.

Patients will be excluded if:

- a) There are craniofacial anomalies including cleft lip/palate,
- b) Patient have previous maxillofacial operations or facial scars,
- c) Correction mandates multi-segment Le Fort I osteotomies,
- d) There are orthodontic appliances in place at the time of T1 records.
- e) Genioplasty is recommended for deformity correction.
- f) There is facial Asymmetry.

All the patients are consented for using their data in research purposes.

The CBCT scans of class III patients who undergone maxillary advancement with minimal or without impaction and mandibular setback will be identified. The preoperative and 6 months postoperative CBCT images will be anonymized and will be saved in a password protected computer. Only the research team members will have access to the research data.

In order to quantify the actual amount of surgical movement, the pre and post-operation CBCT voxel based super imposition using ONDEMAND 3d. The surgical movement will be quantified using direct slice land-marking.

Using the pre-operation CBCT to do the surgical mock up and the soft tissue simulation on dolphin 3D. Soft tissue surface models of the simulation and the actual postoperative images will be generated and exported as STLs.

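### The test is chosen by a normality check but the only interval planned is for mean values, so a signed-rank P value has no matching interval and the two can disagree

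*Combined protocol and SAP*

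**What the plan says.** The Statistical analysis section of the combined protocol and SAP sets a two-stage rule. First, "Numerical data will be explored for normality by checking the distribution of data and using tests of normality", naming Kolmogorov-Smirnov and Shapiro-Wilk. Data judged parametric then go to a paired t-test. Otherwise, "For non-parametric data, Wilcoxon signed-rank test will be used to compare between actual soft tissue measurement and software measurement". The summaries are the mean, median, SD, "minimum, maximum and 95% Confidence Interval (95% CI) for the mean values". No interval is planned for a median or for a signed-rank estimate of shift.

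Four things are not stated: whether the check applies to the paired differences or to each series, what cut-off applies, what happens if the two normality tests conflict, and whether the interval is for the mean difference or for each measurement's own mean.

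The Sample size calculation section starts from "the computed effect size for the accuracy of linear measurements was found to be (1.05") and arrives at 10. It then adds an allowance, "To compensate for 15% for the use of non-parametric tests", and concludes that "the final minimum estimated sample size will be 12 subjects". The Data Analysis section produces summaries for each anatomical region and analyses distances in x, y and z, so the choice of test would be made many times on the same few patients.

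**The concern.** The paired t-test and the interval for the mean difference are two views of one calculation: the P value is at most 0.05 exactly when the 95% interval does not contain zero. The signed-rank test does not have that link to an interval for the mean. Its natural companion is the Hodges-Lehmann estimate, which targets the pseudomedian. Under the plan as written, a region sent to the signed-rank test could be reported as P ≤ 0.05 beside an interval that includes zero, or the reverse, and nothing says which governs.

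An interval for each measurement's own mean would be worse, because it would correspond to neither test. Both tests work on within-patient differences.

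Normality tests have limited power at 12 patients, so which regions are sent to which test would depend partly on chance. Regional results would then not all be estimates of the same quantity.

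**Working it through.** **1. The plan's own sample size.** Inputs from the Sample size calculation section: effect size 1.05 (read as a paired standardised difference), alpha 5% (two-sided assumed), power 80%. Power comes from the noncentral t distribution with n − 1 degrees of freedom and noncentrality 1.05 × √n.

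- n = 10: noncentrality 1.05 × √10 = 3.32, power 83.9%. This is the smallest n above 80%.
- Inflation: 10 × 1.15 = 11.5, or 10 / 0.85 = 11.8. Both round up to 12.
- n = 12: noncentrality 1.05 × √12 = 3.64, power 91.1%.

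The stated 10, then 12, reproduces.

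**2. Simulation of the two-stage rule at n = 12.** Shapiro-Wilk at 0.05 on the paired differences chooses the t-test or the exact signed-rank test. The t interval for the mean is reported in every case. All shapes are assumptions, because the documents give no distribution. There were 40,000 datasets per shape for the first two columns and 15,000 for the shifted cases. *Disagree* means that one of test and interval excludes zero and the other does not.

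| Assumed shape of differences | Sent to signed-rank | t interval covers the mean | Disagree, among signed-rank datasets (shift 0.5 / 0.7 SD) | Disagree, all datasets (shift 0.5 / 0.7 SD) |
|---|---|---|---|---|
| Normal | 4.9% | 94.9% | 9.6% / 10.2% | 0.5% / 0.5% |
| t, 3 df | 21.8% | 95.9% | 16.7% / 19.7% | 3.6% / 4.3% |
| Uniform | 9.5% | 94.7% | 5.7% / 9.3% | 0.5% / 0.9% |
| Half-normal | 23.4% | 93.6% | 3.7% / 9.5% | 0.8% / 2.2% |
| Gamma, shape 4 | 16.3% | 93.7% | 7.1% / 10.8% | 1.2% / 1.8% |
| Lognormal, log-SD 0.5 | 30.4% | 92.4% | 9.1% / 16.1% | 2.8% / 4.8% |
| Exponential | 54.2% | 90.5% | 7.9% / 19.4% | 4.3% / 10.3% |
| Lognormal, log-SD 1 | 70.7% | 85.0% | 25.5% / 12.3% | 17.9% / 8.7% |

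With no true mean difference, disagreement over all datasets runs from 0.1% (normal) to 4.2% (lognormal, log-SD 1). At a shift of 0.6 SD, the exponential and lognormal shapes give about 12% to 26% of signed-rank datasets. Under normality disagreement is rare overall because only about 1 dataset in 20 reaches the signed-rank test.

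**3. Does the choice of test affect coverage?** No. The same interval is reported on either branch, so the coverage column depends on shape alone. For lognormal differences with log-SD 0.5 and 0.8:

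- Coverage of the mean: t interval 92.3% and 88.1%; Hodges-Lehmann interval 92.6% and 87.8%.
- Coverage of the pseudomedian: t interval 94.9% and 95.1%; Hodges-Lehmann interval 95.3% and 95.2%.

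On a common target the two intervals perform alike.

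**4. Exact P values.** For n = 12 the rank sum has null mean 12 × 13 / 4 = 39 and variance 12 × 13 × 25 / 24 = 162.5 (SD 12.75). A rank sum of 14 gives z = (14 − 39) / 12.75 = −1.96 and P = 0.0499 by the normal approximation. The exact P is 0.0522. The two fall on opposite sides of the plan's 0.05 line.

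**The case against.** The strongest defence is that the rule does little harm if the check is made on the differences. Its type I error is 5.1% for normal differences, about 4.6% to 4.8% for t with 3 df, and 4.3% when 1 patient in 10 has a fivefold SD of difference. In that last case, at a shift of 1.05, power is about 71% with the rule, 70% with the signed-rank test always, and 64% with the t-test always. For normal differences the rule keeps 91%, against 88% for the signed-rank test. The plan also reports median, minimum and maximum, so marked skew would be visible. All of this stands, and it limits the point to reporting and wording.

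Three stronger readings are tempting and are not supported.

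- *The check makes the 95% intervals under-cover.* The interval does not depend on the test chosen, so this cannot follow. Samples that pass the check do cover worse in the lognormal cases (about 90% and 81% at log-SD 0.5 and 0.8), but those that fail cover better (97% and 94%). The overall figures are 92% and 88%, and they require skewed differences. Absolute distances are bounded at zero and may well be skewed. The planned tests, however, compare actual with predicted measurements, and the difference of two series skewed alike is symmetric: two independent lognormals give 95.6% and 96.1% coverage.
- *A Hodges-Lehmann interval would restore 95% coverage.* It does so only for the pseudomedian. Making it the sole analysis changes what is estimated.
- *The check is made on the raw series, not the differences.* If so, it could miss outlying differences: in the contaminated case it flags 9% of datasets, against about 35% when the differences are checked. The plan's wording allows this reading but does not state it.

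**Conclusion.** A minor but real gap. The plan chooses a test from the data with low-powered checks, plans an interval that matches only one of the two tests, and leaves open whether that interval is for the paired difference at all. The consequence is possible contradiction between P value and interval within a region, and regional results that do not share one target.

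The size depends on an unknown distribution. Disagreement is at most about 0.5% of datasets if differences are normal. It is about 4% with heavy symmetric tails and a shift of 0.5 to 0.7 SD, and about 12% to 26% of signed-rank datasets under the more strongly skewed shapes at 0.6 SD. Mildly skewed shapes give less: 4% to 11% of signed-rank datasets at 0.5 to 0.7 SD. These figures assume Shapiro-Wilk alone, applied to the differences at 0.05. Coverage of the interval for the mean is near nominal for symmetric differences. Any shortfall comes from skew, not from the choice of test.

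**What to change.** Amend the Statistical analysis section as follows.

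1. For each region and axis, form one paired difference (predicted minus actual) per patient.
2. Base any distribution check, and every interval, on those differences.
3. Report each test with its matching estimate and 95% interval: the paired t-test with the mean difference; the signed-rank test, with exact P values, with the Hodges-Lehmann shift.
4. Preferably name one of the two in advance as primary for all regions and keep the other as a sensitivity analysis. Either choice removes disagreement caused by the choice of test.

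The cost is slightly more reporting. If the signed-rank test is made primary, power under normality at 1.05 SD is 88% instead of 91%, still above the planned 80% and within the allowance already made for non-parametric tests. The target then becomes the pseudomedian instead of the mean, which is a choice the investigators should make knowingly. The minimum of 12 patients is unaffected.

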### **Two dimensional planning and prediction methods:**

The pre-operative planning of orthognathic surgery, and the prediction of the soft tissue changes became highly desirable(3). The early attempts to predict the postoperative profile of patients following orthognathic mandibular surgery is to cut a profile photograph to predict the postoperative appearance. (4,5)

The procedure of digitizing the cephalogram point using computer programs started in the eighties. The technique includes the digitization of the usual cephalometric landmarks by the operator followed by the repositioning of the different parts of the jaw bones using a specialized computer software programs (6,7). The method is more convenient and impresses the patient, but the provided information is no different from the first technique. (8)

However, these studies have focused on the soft-tissue profile as presented on lateral cephalogram, and they do not provide sufficient information to allow an accurate prediction of the postoperative appearance.(8) These Methods were focusing primarily on the lateral cephalogram,(9,10) which is certainly important but of a little direct concern to the patient. Because the patient is often interested in knowing

the details of the expected facial appearance following surgery (10,11) video imaging has the potential to radically improve the nature and sophistication of the pretreatment communication between the patient and the doctor regarding the potential esthetic outcomes of the treatment alternatives being considered.(12,13)

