Authors have used video imaging modalities for soft tissue prediction which provided a significant advance in the field of both orthodontic and orthognathic prediction(5,6). The basic difference lies in the additional step of superimposing the patient's lateral photograph onto the cephalogram (2D computerized prediction). (14,15) the main limitation of these systems is that the computerized prediction of the soft tissue changes following surgery is limited to the profile which is not suitable for the correction of facial asymmetry. It is important for patients to understand that the image produced is a simulation, which may be similar to but not identical with their final facial appearance.(6,16) In spite of its limitations, this latest method has two major advantages over previous techniques.(17) First, the tracing is digitally stored and can be altered more readily than with other methods. The second advantage of video imaging lies in the improvement of the doctor-patient communication(12,15), it promotes greater understanding and satisfaction with the outcome, as long as the patient recognizes that the prediction is only a goal and not a guarantee. Sarver et al (15) have found that 89% of a sample of patients judged video images to be realistic and thought that the goal was achieved. In addition, 83% of patients reported that the prediction helped them to take a decision regarding the proposed treatment modality. Finally, 72% felt that it also allowed them to be an integral part of the treatment process. Similarly, Kiyak and Bell(18) have shown that less than 45% of the patients who did not have video images as part of the treatment planning, were

satisfied with the outcomes of their surgery. Because of the potential impact of video imaging on patient expectations is significant the accuracy of what is being shown becomes critical.(19)

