### **Data Analysis**

Superimposition of the predicted and the post-operative STLs and conformation of the generic meshes will be performed. Using VR mesh software, the mesh will be segmented into pre-identified anatomical regions. The distance between the corresponding vertices will be displayed

as a colour scale in milli-meter and will be analyzed in the individual dimension of space (x, y and z) using in-house software developed for this purpose and each dimension will be displayed as a colour coded distance map. It will be generated to illustrate the magnitude and anatomical regions with prediction inaccuracies analysis. Using this software, the minimum, maximum, mean, standard deviation (SD), absolute maximum, absolute mean, and absolute SD of 90% of the points of each facial anatomical region will be measured.

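### The only planned interval describes the average prediction error; no limits are planned for the error in a single patient

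*Combined protocol and SAP*

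**What the plan says.** The Aim section asks how accurately the software predicts facial soft tissue change, and Study Hypothesis states that predicted and actual results will not differ.

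Statistical analysis lists its summaries in one sentence: "Data will be presented as mean, median, standard deviation (SD), minimum, maximum", followed by the "95% Confidence Interval (95% CI) for the mean values". It then plans a paired t-test, or a Wilcoxon signed-rank test for non-parametric data, of actual against software measurements. It does not say whether the summaries describe the difference between the two or each measurement separately.

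Data Analysis plans further regional summaries in x, y and z, including "absolute maximum, absolute mean, and absolute SD of 90% of the points of each facial anatomical region will be measured". These are taken over mesh points within a facial region.

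Sample size calculation ends with "the final minimum estimated sample size will be 12 subjects". The plan contains no limits of agreement, prediction interval, tolerance interval or proportion of patients within an error limit.

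**The concern.** Accuracy of prediction has two parts: whether the software is wrong on average, and how widely its errors vary from patient to patient. The paired test and the confidence interval for the mean deal with the first. The interval narrows as patients are added, however large the individual errors are.

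Signed errors in x, y and z can also cancel across patients: over-prediction in one offsets under-prediction in another. The introduction warns of this cancellation within a mesh (Comparing pre-operative and post-operative analyses; Analysis based on surface meshes). Statistical analysis has no matching safeguard across patients for signed errors.

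The risk is one of interpretation. A short interval around a small mean error may be taken as evidence that an individual prediction is close, when it shows only that the average error is well estimated.

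**Working it through.** **Inputs from Sample size calculation.** Standardised effect size 1.05, alpha 5%, power 80%, 10 subjects raised by 15% to at least 12.

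**The plan's own figure.** For a two-sided paired t-test with effect size 1.05, exact power is 78.7% at n = 9 and 83.9% at n = 10, so n = 10. Then 10 × 1.15 = 11.5, rounded up to 12. Both figures reproduce if the test is two-sided. The plan does not state sidedness, and a one-sided test would give n = 8.

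**Half-widths at n = 12.** SD is the between-patient SD of the prediction error, and t(0.975, 11) = 2.201.

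- Confidence interval for the mean: t × SD/√n = 2.201/√12 = 0.635 SD.
- 95% prediction interval for one new patient: t × SD × √(1 + 1/n) = 2.201 × √(13/12) = 2.291 SD.
- 95% limits of agreement: 1.96 SD.

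The ratios to the confidence interval are 2.291/0.635 = √13 = 3.61 and 1.96/0.635 = 3.08.

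**Coverage.** In simulation with normal errors, the confidence interval for the mean contains a new patient's error about 45% of the time.

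**Sensitivity to n.** The prediction ratio equals √(n + 1): 3.32 at n = 10, 4.0 at n = 15 and 4.6 at n = 20.

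**In millimetres.** The documents give no between-patient SD, so 1 to 2 mm is an assumption.

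| Assumed SD | CI for the mean | Limits of agreement | Prediction interval |
|---|---|---|---|
| 1 mm | ±0.64 mm | ±1.96 mm | ±2.29 mm |
| 2 mm | ±1.27 mm | ±3.92 mm | ±4.58 mm |

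The introduction cites 2 mm as the usual success level in 3D planning studies; the plan does not adopt it. With normal errors and zero mean error, 2 mm is 1 SD when the SD is 2 mm, so about 32% of patients lie beyond it. It is 2 SD when the SD is 1 mm, so about 5% do. In both cases the confidence interval lies inside ±2 mm.

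**What the planned SD and range give.** If they are computed on the per-patient error, the SD is 1/0.635 = 1.57 times the confidence-interval half-width. Half the expected range is about 2.6 times it. The minimum-to-maximum range contains a new patient with probability 11/13 = 85%.

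If they are computed separately on predicted and actual values, the SD of the error is √(s₁² + s₂² − 2r·s₁·s₂). This requires the correlation r, which is not among the planned summaries.

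**The case against.** The strongest reply is that the sentence naming the confidence interval also plans the SD, minimum and maximum. If these are taken over patients on the prediction error, large individual errors would appear in the same table, and a reader could build a prediction interval from the mean, SD and n. This stands against any claim that individual spread goes unreported. It does not settle the point, because the plan does not say that the summaries are of the paired error. The SD and maximum in Data Analysis do not fill the gap, since they run over mesh points rather than patients.

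Data Analysis also plans absolute means, which do not cancel by sign. That stands, and it limits the cancellation concern to signed x, y and z errors. The confidence interval of an absolute mean still describes an average and still narrows with n.

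A reader might infer that the study exists to tell patients about their own faces, from phrases such as "Because the patient is often interested in knowing" and "the accuracy of what is being shown becomes critical". Both come from background on older profile and video-imaging methods. The stated aim is the accuracy of the software, and for that aim a confidence interval for the mean is legitimate but incomplete.

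A reader might also infer that the software will be made to look 3.6 times more accurate than it is. The documents do not support that. The ratio is the identity √(n + 1), which applies to any confidence interval for a mean, and it is not a bias in any planned estimate.

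**Conclusion.** The point holds as a gap in the planned analysis, not as an error in it. The planned inference concerns average bias. No individual-level limits are prespecified, and the plan does not ensure that its SD and range are those of the per-patient error.

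At n = 12 the confidence interval for the mean is narrower than a 95% prediction interval by a factor of 3.6, and narrower than 95% limits of agreement by a factor of 3.1. It could therefore be misread as individual accuracy.

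These figures assume that the interval is taken over patients (the paired test implies this, but the text does not state it), that n is exactly 12 although 12 is a minimum, and that errors are roughly normal, which may fail for absolute errors. The millimetre figures also rest on the assumed SD of 1 to 2 mm.

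No planned test or estimate is invalidated. The change is worth making because it answers the study's own question better and uses data already to be collected.

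**What to change.** Amend Statistical analysis as follows:

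1. State that the summaries are computed over patients on the per-patient error (predicted minus actual), for each region and axis.
2. Beside the mean and its confidence interval, report either 95% limits of agreement with their own confidence intervals, or a 95% prediction interval (at n = 12, mean ± 2.201 × SD × √(13/12)). For absolute error, give an upper limit computed on the log scale and transformed back.
3. Plot the individual patient values.
4. State that any sentence about accuracy for a single patient rests on these limits, not on the confidence interval for the mean.

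**Cost.** No new patients, scans or measurements are needed, but there are additional columns and plots for every region and axis. The accuracy figure will look less favourable.

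The limits will also be imprecise. The approximate standard error of one limit of agreement is SD × √(1/12 + 1.96²/(2 × 11)) = 0.51 SD. Its 95% confidence interval is therefore about ±2.201 × 0.508 = ±1.12 SD. The limits depend on approximate normality, which about 12 patients cannot test well; the plot of individual values is a partial check.

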### **Comparing pre-operative and post-operative analyses:**

Assessing the accuracy of 3D surgical predictions compared to the actual postoperative result relies on similar techniques of superimposition to 2D, but the method of measurement is potentially more complex. To date, several methods of analysis have been reported including: (1) differences in distance of specific landmarks,(48,49) (2) differences

between all the 3D points of the two entire facial surface meshes,(50,51) and (3) differences between all the 3D points of the two facial surface meshes following division into predefined anatomical regions.(52) Quantitative analysis of each technique involves measuring the linear distances between specific landmarks or between all of the 3D points of the two 3D surface meshes. This can be performed taking into account the direction using the average distance difference, i.e. the signed difference, or irrespective of direction using the absolute Euclidean difference, and finally the root mean square (RMS) difference. The signed differences will cancel out positive and negative values, under-estimating the error; the absolute Euclidean difference will ignore the direction and only report the magnitude.

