### **Analysis based on surface meshes**

#### Pre and post-operative image registration for comparison:

The analysis of 3D surface polygonal meshes is one method of assessing topographical and positional surface changes in 3D. To assess the accuracy of the software-derived prediction compared to the actual final soft tissue image, registration or superimposition of the two images is required. This can be achieved using two methods. The first involves maintaining the existing hard and soft tissue relationship of each of patient's prediction and actual images and then superimposing the hard tissues on the anterior cranial base. As the hard and soft tissue relationship is 'locked', following hard tissue alignment, the soft tissues will also be aligned relative to their hard tissue position. The distance between the two soft tissue surfaces can then be analyzed. The second option is to ignore the underlying hard tissue and use the forehead region of the soft tissue only to align the two images. The results may be different, especially if the patient has lost adipose tissue from around the upper face region; this will

be immediately apparent if the images are aligned on the skull but not if they are aligned on the soft tissue only. Alignment of the images relying on the soft tissue only may also be difficult as there is less surface topography for the images to reliably align on.

Following alignment of the images, the distance between the two surfaces can be determined. The current method is based on the distance between one point on one surface and the closest point to it on the second surface. Note that the measurement relies on the closest point, which may not necessarily be the corresponding anatomical point. Unless the surface meshes are identical, there will be some points on one mesh where the closest point on the second mesh is absent, but the algorithm finds an inappropriate point on the second mesh and produces a large incorrect reading. To overcome the effects of these ‘outliers’, some studies ‘filter-out’ the values by using the 95th and 90th percentiles.(50–52)

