As the facial surface mesh is made up of thousands of points, an overall mean value for the error is often reported. If one facial surface mesh is totally in front of the other, all the distance measurements will be either positive or negative and therefore the mean is valid. If however some parts of one mesh lie behind and some in front of the other mesh, distance measurements for the whole face will be made up of positive and negative values. Any positive values will cancel out any negative values under-estimating the mean difference and so biasing the results. In order to overcome this problem, some studies use the absolute mean values or Euclidean distances, which ignore the sign (direction) and report on the magnitude of error or the RMS error. The RMS error is derived from all the points making up the surface mesh which makes it not clinically useful, as the site of the error remains unknown; however, dividing the face into anatomical regions and analyzing them separately immediately focuses on

the areas of error. Many studies assess the accuracy of the prediction by comparing the differences in distance between the prediction and the actual surfaces using the entire face, including the areas that have been used for alignment, i.e. the areas with minimal change. Therefore a large percentage of the mesh has minimal or no change; this will bias the accuracy by reducing the impact of the error—the data will be skewed towards the smaller values. In order to overcome this, areas of the face used for alignment can be excluded and the remaining mesh divided into anatomically relevant regions this method highlights the true level of error in the predictive ability of the package.

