## **The Aim**

The aim of the present study is to evaluate the accuracy of Dolphin 3D software in the prediction of facial soft tissue changes after bimaxillary orthognathic surgery.

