### ***Study Hypothesis***

There will be no difference between actual soft tissue results and Dolphin 3D software soft tissue prediction.

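### The only test of prediction against outcome is a paired difference test not linked to any planned measurement, so a non-significant result cannot support the no-difference hypothesis or show accuracy

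*Combined protocol and SAP*

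**What the plan says.** The Aim is to "evaluate the accuracy of Dolphin 3D software in the prediction of facial soft tissue changes". The Study Hypothesis is: "There will be no difference between actual soft tissue results and Dolphin 3D software soft tissue prediction".

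The Data Analysis section superimposes the predicted and postoperative surfaces, divides the mesh into anatomical regions that it does not list, and analyses the distances between corresponding vertices along x, y and z. It then takes seven summaries per region, some signed and some absolute, ending with: "absolute maximum, absolute mean, and absolute SD of 90% of the points of each facial anatomical region will be measured".

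The Statistical analysis section plans means with 95% confidence intervals. It then gives a paired t-test for parametric data and, for other data, "Wilcoxon signed-rank test will be used to compare between actual soft tissue measurement and software measurement", at a 5% significance level. It names no variable, region, axis or summary for that test and does not refer back to the Data Analysis section.

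The Sample size calculation uses a standardised effect of 1.05, 5% alpha and 80% power to reach 10 subjects, then adds 15% to reach 12. It mentions a target of 90% accuracy without defining it in mm, and the target does not reappear. The literature review reports that most 3D planning studies used a success level below 2 mm. This study does not adopt that level.

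**The concern.** Two things do not fit together. First, a paired test needs two values per patient, but the measurements described are distances from prediction to outcome and so are already differences. The reader cannot tell which pair enters the test, and nothing is marked as primary.

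Second, on the natural reading (signed distances, or paired coordinates) the test asks whether the average error across patients is zero. That is bias, not accuracy: a software package that is 3 mm too far forward in half the patients and 3 mm too far back in the rest has no bias. The protocol makes the same point about a single face: "The signed differences will cancel out positive and negative values, under-estimating the error", and again "Any positive values will cancel out any negative values under-estimating the mean difference and so biasing the results". The arithmetic is the same across patients.

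At stake is the main conclusion. The hypothesis is worded as no difference, and the only test available can fail to reject because the sample is small or because the errors are large and scattered. The descriptive summaries could answer the aim, but region, axis, summary and acceptable limit could all be chosen after the data are seen.

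**Working it through.** **Inputs.** From the Sample size calculation: effect size 1.05, alpha 5%, power 80%, n = 10 raised to 12. Sidedness is not stated. The documents give no soft-tissue bias, SD or limit in mm, so every mm value below is an assumption.

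**1. The plan's own figure.** Two-sided paired t-test, noncentral t with n − 1 degrees of freedom and noncentrality d√n.
- n = 9: 1.05 × 3 = 3.15, power 0.787.
- n = 10: 1.05 × 3.162 = 3.32, power 0.839.

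So n = 10 reproduces (a one-sided test would give 8). The 15% allowance gives 10 × 1.15 = 11.5 or 10 / 0.85 = 11.8, either way 12, where power is 0.911. The arithmetic is sound, but it is the size needed to detect a difference of 1.05 SD.

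**2. What a non-significant result means at n = 12.** The probability of P > 0.05 is 84% for a true bias of 0.3 SD, 65% for 0.5 SD, 29% for 0.8 SD and 9% for 1.05 SD. The smallest bias detectable with 80% power is 0.89 SD. The 95% CI half-width is about 2.201 / √12 = 0.64 SD.

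**3. Does the test follow the size of the error?** Take one axis and one error per patient, normal with bias b and SD s. Then E|e| = s√(2/π)·exp(−b²/2s²) + b[1 − 2Φ(−b/s)], and power follows from d = b/s at n = 12.

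| Bias (mm) | SD (mm) | d | Mean absolute error (mm) | Errors over 2 mm | Chance of significance |
|---|---|---|---|---|---|
| 0.5 | 0.5 | 1.0 | 0.58 | 0.1% | 88% |
| 0.5 | 1 | 0.5 | 0.90 | 7% | 35% |
| 0.5 | 2 | 0.25 | 1.65 | 33% | 12% |
| 0 | 1 | 0 | 0.80 | 5% | 5% |
| 0 | 2 | 0 | 1.60 | 32% | 5% |
| 0 | 3 | 0 | 2.39 | 50% | 5% |

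In the first three rows prediction gets worse while significance becomes less likely. In the last three the test is silent whatever the error size.

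**4. Does the choice of summary matter?** The literature review says that some studies remove outlying distances: "the values by using the 95th and 90th percentiles". The Data Analysis section does not say which 90% of points are kept. If the largest 10% are dropped and vertex errors are normal around zero, the mean absolute distance is multiplied by 0.824 on one axis (an 18% fall) or 0.910 in 3D (a 9% fall). With three independent, equal axes and no bias, the mean 3D distance is twice the one-axis value. A mm limit therefore has meaning only for a fully specified variable.

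**5. What a rule against a bound would deliver at n = 12.** Assume a 2 mm bound, a one-sided 5% one-sample t-test, and d = (2 − mean)/SD with SD 1.0 mm.
- Mean 1.0 mm: d = 1.0, power 0.94 (8 patients for 80%).
- Mean 1.5 mm: d = 0.5, power 0.49 (27 patients for 80%).

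These use a normal model, but absolute distances cannot be negative and are likely to be skewed. Simulating a gamma distribution with mean 1.0 and SD 1.0 gives power of about 0.87. With the true mean exactly at 2 mm, the t-based limit then declares accuracy in about 8%, 10% and 13% of studies at SD 1, 1.5 and 2 mm, not the nominal 5%.

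**The case against.** The strongest reply is that the aim is to evaluate accuracy, which is an estimation task. Regional absolute means, SDs and maxima are planned, with 95% CIs for means, and no pass/fail verdict is required. That stands. A reader might infer that the study as planned cannot answer its aim at all. The documents do not support this, because the descriptive output can answer it. What fails is the test as support for the hypothesis.

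A reader might also infer that the investigators will read P > 0.05 as proof of accuracy. No section says so, and the hypothesis can be read as an ordinary null. The problem is that nothing rules this reading out and no other decision rule is given.

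A third tempting step is to say that the test would always reject, since 12 positive distances against zero give an exact Wilcoxon P of 2/2¹² = 0.0005. The arithmetic is right, but the plan does not state that analysis.

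Other replies stand in part. Axes and regions are mentioned in the Data Analysis section, so what is missing is the link to the test and a primary choice. Absolute summaries by region largely answer the within-face cancellation warning; the extension to cancellation between patients concerns the test only. The zero-bias rows are non-significant 95% of the time by construction. At a fixed SD the test does respond to bias: with SD 1 mm, power is 0.35 at 0.5 mm and 0.88 at 1 mm. Finally, a bound-based rule judges the average patient: with mean and SD both 1.0 mm, some 14% (gamma) to 16% (normal) of patients still exceed 2 mm.

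**Conclusion.** The concern holds in limited form. The planned paired test has no defined variable and, on signed values or coordinates, examines mean bias only. At n = 12 it misses a bias of 0.5 SD about 65% of the time, and for a fixed non-zero bias it becomes less likely to be significant as errors grow more variable. A non-significant result cannot support the no-difference hypothesis or show accuracy. The summaries that could show error size are planned, but they are neither primary nor given a limit.

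The miss rates in SD units follow from n = 12 and normal paired differences. The mm figures rest on assumed biases and SDs and are illustrations. The direction of the effect does not depend on the particular values. The sample size is not miscalculated; it answers a different question from the one the hypothesis poses.

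**What to change.** 1. Make the primary analysis one value per patient: the mean absolute distance between corresponding vertices in one named primary region. State whether it is 3D or per axis and which 90% of points are kept. Report it with a 95% CI and the share of patients within a stated mm limit. Treat the other regions as secondary.
2. Keep the paired test, with signed x, y and z means and CIs, as a secondary analysis of bias. State the variable it uses, and that P > 0.05 is not evidence of accuracy.
3. Only if the study is to declare the prediction accurate, pre-specify and justify a soft-tissue mm bound and require the upper one-sided 95% confidence limit to lie below it. The 2 mm level in the literature review is a candidate only, since it comes from 3D planning studies. Use a method suited to skewed, non-negative data, such as a log-scale or bootstrap limit, and check its error rate at n = 12.
4. State that 12 patients were sized to detect a difference of 1.05 SD, and restate the precision or power of the new primary analysis at that size.

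The cost is a short rewrite before any scan is analysed, plus the work of justifying a limit. No new measurements are needed, because the vertex distances are already planned. Stated power may be less favourable: with an assumed 2 mm bound and SD 1.0 mm, about 0.87 to 0.94 if the true mean is 1.0 mm and about 0.5 if it is 1.5 mm. In the latter case more existing scans would be needed to reach 80%.
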